1.5. SM-88 Clinical Data

Preliminary data suggest that SM-88 used with MPS/M2PS is efficacious in a variety of metastatic malignancies. Data from the FIH study of SM-88 (Stega, Noel et al. 2019) and a robust compassionate use program (Zhu, Noel et al. 2018, Zhu, Noel et al. 2018) demonstrate confirmed responses in patients with a variety of metastatic cancers including HR+/HER2- breast cancer. All patients in the FIH study and the compassionate use program had progressive metastatic cancer prior to receiving SM-88. Among 30 patients (14 breast, 5 lung, 3 pancreas, 2 prostate, and 1 each of colon, tongue, thyroid, liver, appendix, and biliary) in the FIH study, 10 (33%) experienced an objective response (OR), 4 patients had a complete response (CR), 3 of whom had HR+/HER2- breast cancer, and 6 patients had a partial response (PR), 3 of whom had breast cancer. Among patients who had an OR, time to best response ranged from 1.5-15.5 months with the majority occurring after 3 months of treatment, indicating that long term administration of SM-88 may be needed to achieve full therapeutic potential. An additional 17 patients had stable disease (SD) with a median duration of 11 months (range 1-31 months). Median progression-free survival (PFS) was 13 months and median overall survival (OS) was 29.8 months. Thirteen patients had responses lasting > 12 months and six patients had responses lasting > 24 months. Since there was no control group in this study, an exploratory analysis comparing each patient's penultimate PFS (PFS on standard treatment before enrollment in the study) to PFS on the investigational treatment. The median penultimate PFS was 4 months (95% CI: 3-8, KM estimate) while the median PFS on study was 11 months (95% CI: 6-26, KM estimate) ($p = 0.0021$, log-rank test), which suggests that SM-88 therapy may provide clinical benefit. The majority of patients (N = 25, 83%) had an improvement in ECOG performance status by the end of cycle 1. Following treatment in the FIH study, 13/30 (43%) patients went on to receive subsequent cancer therapy (chemotherapy, radiation, or surgery). The breast cancer patients had been treated with an average of 2.5 prior

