4.3.9. Tumor assessment

Patients must have measurable disease, defined as at least 1 unidimensionally measurable lesion as defined by RECIST v1.1 (tumor \geq 1 cm in longest diameter on axial image on CT or MRI, tumor \geq 10 mm by caliper measurement on clinical exam and/or lymph node(s) \geq 1.5 cm in short axis on CT or MRI). This includes lytic bone lesions or mixed lytic-blastic lesions with an associated soft tissue component \geq 10mm noted on CT or MRI as per RECIST v1.1. I. Index lesions cannot have been previously treated with local therapy, such as radiation.

Baseline imaging must be performed within 28 days of initiating therapy. Ideally, this will include a CT scan of the chest, abdomen, and pelvis with IV contrast, or can consist of an MRI of the chest, abdomen, and pelvis or

positron emission tomography (PET) scan with diagnostic non-contrasted CT of the chest, abdomen, and pelvis for patients who cannot undergo a contrast-enhanced CT scan. Bone scan will be done at screening and repeated only if clinically indicated or at the treating physician's discretion. If a patient has an allergy to IV contrast, appropriate pre-medication can be given to prevent a contrast reaction. Patients may undergo other modalities such as an MRI instead of a CT scan at the treating physician's discretion if appropriate (such as severe allergy to CT contrast, extremity tumors, bone metastases requiring bone scans, etc.).

Patients will receive therapy until disease progression, as per RECIST v1.1 criteria, or therapy intolerance. Response assessment will occur every 8 weeks (+/- 7 days), attempting to occur close to the start of a new cycle. If there are any significant delays, restaging exams must not occur more than 12 weeks (+/- 7 days) apart. For patients who achieve a CR, PR, or SD (as demonstrated by RECIST v1.1) confirmed on two consecutive restaging scans, restaging scans may transition to every 12 weeks. Re-staging CT scan of the chest, abdomen, and pelvis with IV contrast, MRI of the chest, abdomen, and pelvis, or positron emission tomography (PET) scan with diagnostic non-contrasted CT of the chest, abdomen, and pelvis will be repeated every 8 weeks (+/- 7 days), or 12 weeks (+/- 7 days) if the patient has achieved CR, PR or SD on two consecutive restaging scans. Bone scan is optional. Only patients with SD, PR, or CR, as demonstrated by RECIST v1.1 will continue on treatment per protocol.

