¹¹ End of Treatment visit should occur as soon as possible at the time of progression or discontinuation of treatment, preferably before the subject starts the next therapy, + 10 days from last dose. Imaging and tumor assessments do not need to be performed at this visit if performed within 30 days prior to the visit.

¹² Bone scan at investigator discretion

¹³ Long term follow up assessment (+/- 4 weeks). Patients will be contacted by phone call or e-mail for vital status data collection, adverse events evaluation (if AEs from study have not yet been closed), subsequent anti-breast cancer therapy (systemic therapy, radiation, or surgery), and development of a secondary malignancy.

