7.4.1.2. Partial Response (PR)

A 30% or more decrease in the sum of the LD of target lesions that have been measured to determine the effect of therapy by two observations not less than 4 weeks apart. There can be no appearance of new lesions.

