7.5. Evaluation of Best Overall Response

The best overall response is the best response recorded from the start of the treatment until disease progression/recurrence (taking as reference for progressive disease the smallest measurements recorded since the treatment started). The patient's best response assignment will depend on the achievement of both measurement and confirmation criteria.

Table 6. Response Evaluation

Target Lesions	Non-Target Lesions	New Lesions	Overall Response	Best Response for this Category Also Requires:
CR	CR	No	CR	>4 wks confirmation
CR	Non-CR/Non-PD	No	PR	>4 wks confirmation
PR	Non-PD	No	PR	
SD	Non-PD	No	SD	Documented at least once >4 wks from baseline

PD	Any	Yes or No	PD	no prior SD, PR or CR
Any	PD*	Yes or No	PD	
Any	Any	Yes	PD	

* In exceptional circumstances, unequivocal progression in non-target lesions may be accepted as disease progression.

Note: Patients with a global deterioration of health status requiring discontinuation of treatment without objective evidence of disease progression at that time should be reported as "symptomatic deterioration". Every effort should be made to document the objective progression even after discontinuation of treatment.

Note: If patients respond to treatment and are able to have their disease resected, the patient's response will be assessed prior to the surgery.

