8.3. Sample Size Considerations

This proposed phase II study will utilize the Simon's minimax two-stage design (Simon 1989). The desirable ORR is 20% (based on the ORR of 19.7% seen with abemaciclib monotherapy in the MONARCH 1 Phase II clinical trial, which was conducted in \geq 3rd line treatment of metastatic HR+/HER2- breast cancer)(Dickler, Tolaney et al. 2017) and the undesirable ORR of 9.5% (based on ORR of 9.5% seen in a trial of exemestane plus everolimus in the Phase III BOLERO-2 study in patients who had progressed on a non-steroidal aromatase inhibitor and had a median of 3 previous therapies) (Baselga, Campone et al. 2012).

The null hypothesis is that the true response rate is 0.095, and the alternative hypothesis is that the true response rate is 0.2. The trial is carried out in two stages. In Stage 1, a total number of 30 patients is accrued. If there are 2 or fewer responses among these 30 patients, the study will be stopped early. Otherwise, additional 20 patients will be accrued in Stage 2, resulting in a total number sample size of 50. If there are 8 or more responses among these 50 patients, we reject the null hypothesis and claim that the treatment is promising. The design controls the type I error rate at 0.1 with a power of 0.8.

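### No confirmatory scan is scheduled, so a first response seen after the optional move to 12-weekly imaging waits about 12 weeks for confirmation instead of 8, and the primary response count depends on that choice

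*Combined protocol and SAP*

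**What the plan says.** **Confirmation.** Section 7.4.1.2 requires a PR to be established "by two observations not less than 4 weeks apart". Section 7.4.1.1 sets the same minimum for CR. Neither sets a maximum gap. Section 7.5 adds: "The patient's best response assignment will depend on the achievement of both measurement and confirmation criteria".

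**Scan schedule.** Section 4.3.9 sets restaging every 8 weeks (+/- 7 days). Once CR, PR or SD is "confirmed on two consecutive restaging scans, restaging scans may transition to every 12 weeks". The synopsis, Sections 4.1 and 4.5 and footnote 6 of the Study Calendar carry the same option, and none says which patients should move. Section 4.1 ties scans to the calendar. No section schedules a confirmatory scan after a first response, or returns a new responder to 8-weekly imaging.

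**Decision rule.** Section 8.3 states: "The null hypothesis is that the true response rate is 0.095", and "the alternative hypothesis is that the true response rate is 0.2". The trial continues with 3 or more responses in 30 and succeeds with 8 or more in 50. "The design controls the type I error rate at 0.1 with a power of 0.8". Section 8.4.1 defines ORR as PR plus CR and does not mention confirmation timing.

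**Expected timing.** Section 1.5 reports that in the first-in-human study "time to best response ranged from 1.5-15.5 months with the majority occurring after 3 months of treatment".

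**The concern.** With no dedicated confirmatory scan, the next routine scan does the confirming. How long a response must last to count then depends on the patient's scan interval. A patient with two SD scans may be on either interval, at the discretion of whoever schedules the imaging, so two patients with the same tumor course can be scored differently on the primary endpoint.

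Late responders are the ones most likely to have two SD scans first, and the protocol's own background leads one to expect delayed responses. The success threshold is 8 of 50, so a single unconfirmed responder can decide the trial.

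**Working it through.** **1. Reproduce the design.** Inputs from Section 8.3: p0 = 0.095, p1 = 0.20; stop at 2 or fewer of 30; succeed at 8 or more of 50.

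P(success | p) = sum over x = 3 to 30 of P(X1 = x) × P(X2 ≥ 8 − x), with X1 ~ Bin(30, p) and X2 ~ Bin(20, p).

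This gives 0.0955 at p = 0.095 and 0.802 at p = 0.20. Both agree with the stated limits of 0.1 and 0.8.

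**2. Lay out the calendar for a patient with SD at weeks 8 and 16.**

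| Schedule | Scan weeks | Example first PR | Next scheduled scan | Gap |
|---|---|---|---|---|
| Stays 8-weekly | 8, 16, 24, 32, 40 | 24 | 32 | 8 weeks |
| Moves to 12-weekly | 8, 16, 28, 40, 52 | 28 | 40 | 12 weeks |

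The 7-day window on the second scan makes the longer gap about 11 to 13 weeks. The definition itself needs only 4.

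**3. Size of the effect (illustration).** The documents give neither response duration nor the share of late first responses. Assumptions:

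- 20% is the ORR confirmable when everyone is scanned 8-weekly.
- Duration after first detection is exponential, with median M of 6 months (range 4 to 12).
- A share f of responders, 50% (range 30% to 70%), is first seen on the 12-week grid.
- Every late responder has switched.

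Only the confirmation step is modelled. With S(t) = 2^(−t/M) and 4.348 weeks per month, the ratio S(12)/S(8) = 2^(−4/M), M in weeks, and

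confirmed ORR = 0.20 × [(1 − f) + f × 2^(−4/M)].

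| M | f | 2^(−4/M) | Confirmed ORR | Expected responders in 50 | Power |
|---|---|---|---|---|---|
| all 8-weekly | – | – | 20.0% | 10.0 | 0.80 |
| 12 months (52.2 wk) | 0.3 | 0.948 | 0.20 × (0.7 + 0.3 × 0.948) = 19.7% | 9.8 | 0.79 |
| 6 months (26.1 wk) | 0.5 | 0.899 | 0.20 × (0.5 + 0.5 × 0.899) = 19.0% | 9.5 | 0.75 |
| 4 months (17.4 wk) | 0.7 | 0.853 | 0.20 × (0.3 + 0.7 × 0.853) = 17.9% | 9.0 | 0.69 |

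**4. Uptake.** If only half of the late responders switch, the central case becomes 0.20 × [0.75 + 0.25 × 0.899] = 19.5%, with power 0.78.

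**5. Direction under the null.** The same factor applied to 9.5% gives 0.095 × 0.950 = 9.0% in the central case. The chance of success falls from 0.0955 to 0.076, so type I error is not inflated.

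**The case against.** **Earlier confirmation is not barred.** The definition needs only 4 weeks, unscheduled scans are allowed, and Section 7.1 accepts physical-exam measurement, so superficial lesions could be confirmed at a 4-weekly visit. This stands: the 12-week wait belongs to scheduled imaging. But earlier confirmation is not required either, so the count still depends on local practice.

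**The loss may be small.** Section 1.5 reports time to best response, not first response. A week-8 PR that later deepens is late there but is confirmed on the 8-week grid. Three months is also well short of week 28, the first scan on the 12-week grid. So Section 1.5 makes late first responses plausible but does not establish a 50% share. It also mentions thirteen patients with responses beyond 12 months. That exceeds the ten objective responders and may include stable disease, but it hints at long durations. With half late and medians of 12, 18 and 24 months, power is 0.776, 0.785 and 0.789. This limits the size, not the inconsistency.

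**Stronger readings that do not hold.**

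- A reader might take 20% as the ORR confirmable at the 4-week minimum and infer power of 0.63 in the central case. Power is already 0.69 there with everyone scanned 8-weekly, so about 0.11 of the 0.17 drop has nothing to do with the switch.
- A reader might infer that power is lost for late responders as a group. Power belongs to the trial, not to a subset of its responders.
- A reader might infer that footnote 11 turns a PR seen shortly before a toxicity stop into a non-response, since "Imaging and tumor assessments do not need to be performed at this visit if performed within 30 days prior to the visit". That waiver is permissive and applies under 8-weekly scanning too. Sections 3.6.2.1 and 4.3.12.2 may make such a patient non-evaluable and replaced. Requiring a later scan would also sit badly with the 10-day End of Treatment window and with Section 4.3.12.1, under which final procedures must not hold up new therapy.

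**Conclusion.** The point holds in a limited form. As written, the schedule makes confirmation of a first CR or PR on the 12-week grid wait about 12 weeks, against 8 on the default grid, and the choice between the two is open. The primary count therefore depends on an optional interval.

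The bias is conservative. On the stated assumptions, power is 0.69 to 0.79 instead of 0.80, with a central value of 0.75. These are upper bounds on the loss for those inputs, because they assume every late responder switches. Nothing here invalidates the design, whose error rates reproduce. This is a cheap improvement, not a fatal fault.

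**What to change.** Add to Section 4.3.9, and carry into the synopsis, Sections 4.1 and 4.5 and footnote 6 of the Study Calendar:

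> The tumor assessment after a first CR or PR is done at least 4 weeks and no later than 8 weeks (+/- 7 days) after it; 12-week spacing may be used only when no CR or PR is awaiting confirmation.

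This uses the protocol's own default interval and keeps 12-weekly imaging for everyone with no response pending. In the same amendment, reconcile Section 7.1, which still describes assessments every 12 weeks after baseline, with the 8-weekly schedule elsewhere. No change to footnote 11 is proposed.

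Cost: protocol wording. For the few late responders one scan moves about 4 weeks earlier, with at most one extra scan each.

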4.3.10. Adverse Event Assessment

Baseline symptoms at Cycle 1 Day 1 (prior to initiating therapy) should be detailed and graded. Once treatment has started, adverse events will be assessed every 4 weeks on Day 1 (+/- 7 days). The individual Investigator should record any adverse event in detail including the date of onset, event diagnosis (if known) or sign/symptom, severity, time course, duration and outcome, relationship of the adverse event to study drug, and any action(s) taken. For serious adverse events not considered "probably related" to study drug, the Investigator will provide an "Other" cause of the event. For adverse events to be considered intermittent, the events must be of similar nature and severity. See Section 6.5 for Adverse Event monitoring and reporting. The Principal Investigator or sub-Investigators will assess adverse events, laboratory data and vital signs throughout the study. Adverse events will be assessed by NCI CTCAE Version 5.0. Adverse events, whether in response to a query, observed by site personnel, or reported spontaneously by the patient will be recorded. All adverse events will be followed to a satisfactory conclusion.

4.3.11. Correlative Blood Samples

Correlative blood samples will be obtained at time frames detailed below in Section 9.

4.3.12. Removal of Patients from Study Treatment

Each patient has the right to withdraw from study treatment at any time. In addition, the Investigator may discontinue a patient from the study treatment at any time for any reason if the Investigator considers it necessary, including the occurrence of an adverse event or noncompliance with the protocol. Each patient will be withdrawn from study treatment if any of the following occur:

- 1) The patient experiences either clinical or radiographic progressive disease.
- 2) The patient requires radiotherapy or alternate antineoplastic agents during the study period.
- 3) The Investigator believes it is in the best interest of the patient.
- 4) Clinically significant deterioration of the patient's medical status as determined by the Investigator.
- 5) Patient becomes pregnant or begins breastfeeding or partner becomes pregnant during the treatment portion of the study.
- 6) Any other medical reason that the study Investigator deems appropriate.

Note: If a patient requires one of the MPS conditioning agents to be discontinued, treatment with the other study medications may be continued at the discretion of the Investigator in consultation with Sponsor. If a patient requires SM-88 to be discontinued, treatment with the other study agents (MPS) will also be discontinued.

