3.6.2. Evaluable Patients

3.6.2.1. Objective Response Evaluable

To be considered evaluable for the primary endpoint of ORR as determined by RECIST v1.1, the patient must meet all inclusion/exclusion criteria and remain on study treatment at least until the first re-staging after cycle 2 of SM-88 used with MPS unless they are taken off for disease progression, clinical progression, or death related to the underlying solid tumor malignancy (as determined by the treating oncologist) in which case they **will be** deemed evaluable. However, patients who have initiated therapy and who withdraw from the study for any reason other than clinical or radiographic progression, or death believed unrelated to their underlying solid tumor malignancy **will not be** considered evaluable for response. Reasons for patients who have initiated therapy, but are no longer evaluable for response could include (but are not limited to):

- The patient cannot tolerate therapy despite dose modifications, and there is no evidence of clinical/radiographic disease progression at the time of stopping therapy
- An unexpected and/or unrelated medical illness, such as a stroke or myocardial infarction that is considered unrelated to the underlying solid tumor malignancy
- An unexpected trauma or death that is considered unrelated to the underlying solid tumor malignancy

If a patient is deemed to be non-evaluable for the primary endpoint of ORR they will be replaced.

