4.3.12.2. Patient Replacement Criteria

To be considered evaluable for the primary endpoint of ORR as determined by RECIST v1.1, the patient must meet all inclusion/exclusion criteria and remain on study treatment at least until the first re-staging after cycle 3 of SM-88 used with MPS unless they are taken off for disease progression, clinical progression, or death related to the underlying solid tumor malignancy (as determined by the treating oncologist) in which case they **will be** deemed evaluable. However, patients who have initiated therapy and who withdraw from the study for any reason other than clinical or radiographic progression, or death believed unrelated to their underlying solid tumor malignancy **will not be** considered evaluable for response. Reasons for patients who have initiated therapy, but are no longer evaluable for response could include (but are not limited to):

- The patient cannot tolerate therapy despite dose modifications, and there is no evidence of clinical/radiographic disease progression at the time of stopping therapy
- An unexpected and/or unrelated medical illness, such as a stroke or myocardial infarction that is considered unrelated to the underlying solid tumor malignancy
- An unexpected trauma or death that is considered unrelated to the underlying solid tumor malignancy

If a patient is deemed to be non-evaluable for the primary endpoint of ORR they will be replaced.

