7.6. Definition of Disease Progression

Disease progression will be defined as:

- Progression of disease by RECIST v1.1 criteria.
- Clinical progression as determined by the Investigator, which may be characterized as, but is not limited to:
 - Increase of at least 2 points in ECOG performance status attributable to cancer progression.
 - Requirement for palliative chemotherapy or surgery.
- Death from any cause that is not unequivocally unrelated to disease progression (e.g. motor vehicle accident)

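### Patients withdrawn early for radiotherapy or another anticancer drug have no stated status for ORR, and the evaluability rules allow them to be replaced rather than counted as non-responders

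*Combined protocol and SAP*

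**What the plan says.** Section 4.3.12 lists the events that end study treatment. Item 1 is "The patient experiences either clinical or radiographic progressive disease". Item 2, a separate entry, is "The patient requires radiotherapy or alternate antineoplastic agents during the study period".

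Section 7.6 defines progression as RECIST v1.1 progression, clinical progression, or death not clearly unrelated to the disease. The clinical part is introduced by "Clinical progression as determined by the Investigator, which may be characterized as, but is not limited to". It then gives two examples: "Increase of at least 2 points in ECOG performance status attributable to cancer progression" and "Requirement for palliative chemotherapy or surgery". Radiotherapy is not named, nor are anticancer drugs other than chemotherapy. Section 3.4.2, by contrast, counts radiotherapy, endocrine therapy, immunotherapy and biologic therapy as anti-tumor treatment.

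Section 3.6.2.1 makes a treated patient non-evaluable for ORR if that patient is among those "who withdraw from the study for any reason other than clinical or radiographic progression", and adds: "If a patient is deemed to be non-evaluable for the primary endpoint of ORR they will be replaced". Section 4.3.12.2 repeats both rules, but ends the evaluability window at the re-staging after cycle 3, where 3.6.2.1 has cycle 2. Section 7.1.1 repeats the non-evaluable rule without the replacement sentence.

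Section 8.4.1 computes ORR in every patient with one cycle or more of the combination and sets no evaluability condition. Section 8.3 gives the design: 30 patients, continue with 3 or more responses; 50 patients in total, success with 8 or more; null 9.5%, alternative 20%, type I error 0.1, power 0.8.

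**The concern.** A patient who needs radiotherapy for a symptomatic lesion, or another anticancer drug for worsening disease, before the first scan has in ordinary terms failed treatment. The plan does not say how that patient counts. Item 2 stands apart from item 1, so it is not progression by definition. Whether the patient enters the denominator then depends on whether the investigator also records clinical progression. The trial is open-label and single-arm, and under 7.3 the same investigator assesses response.

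The bias runs one way. First re-staging is at week 8, and CR and PR each need two observations at least 4 weeks apart (7.4.1.1, 7.4.1.2). A patient who leaves before first re-staging therefore has no confirmed response. Replacing that patient removes a non-responder and puts in someone who may respond. Measurable bone-only disease is eligible, so radiotherapy to a bone lesion is a realistic route. What is at stake is the meaning of the 3-of-30 and 8-of-50 thresholds, since the design has little spare type I error.

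**Working it through.** **1. The plan's own figures.** Inputs from 8.3: p0 = 0.095, p1 = 0.20, stage 1 n = 30 (continue if 3 or more), total n = 50 (success if 8 or more).

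P(success | p) = Σ over x = 3 to 30 of P(Bin(30, p) = x) × P(Bin(20, p) ≥ 8 − x)

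At p = 0.095:

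| Stage 1 responses x | P(x) | P(enough in stage 2) | Product |
|---|---|---|---|
| 3 | 0.2351 | 0.0357 | 0.0084 |
| 4 | 0.1666 | 0.1156 | 0.0192 |
| 5 | 0.0909 | 0.2947 | 0.0268 |
| 6 | 0.0398 | 0.5790 | 0.0230 |
| 7 | 0.0143 | 0.8642 | 0.0124 |
| 8 or more | 0.0057 | 1 | 0.0057 |

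The products sum to 0.0955. The same formula at p = 0.20 gives 0.802. The stated type I error limit and power both reproduce, and a search over designs confirms this one as the minimax design. The room left below 0.10 is 0.10 − 0.0955 = 0.0045.

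**2. How an early exit is classified.** Take a patient who leaves before first re-staging because of 4.3.12 item 2:

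| Finding at exit | 3.6.2.1 / 4.3.12.2 | 8.4.1 |
|---|---|---|
| RECIST progression documented | Evaluable non-responder | In denominator if at least one cycle |
| No RECIST progression; investigator records clinical progression | Evaluable non-responder | In denominator if at least one cycle |
| No RECIST progression; clinical progression not recorded | Non-evaluable, replaced | In denominator if at least one cycle |
| Same as the row above, but less than one cycle taken | Non-evaluable, replaced | Not in denominator |

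The last two rows are the gap. In the third row the sections contradict each other. In the fourth the patient is lost under both texts.

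**3. Effect on the test.** Let d be the fraction of treated patients who are replaced by this route, all of them non-responders, with d equal in both stages. If ORR in all treated patients is p, ORR in the replaced set is p / (1 − d), and filling 50 places takes on average 50 / (1 − d) treated patients. The documents give no value for d, so the range is an assumption. With p = 0.095:

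| d | ORR in replaced set | Treated to fill 50 | P(success) |
|---|---|---|---|
| 0 | 9.50% | 50.0 | 0.0955 |
| 1% | 9.60% | 50.5 | 0.100 |
| 2% | 9.69% | 51.0 | 0.104 |
| 5% | 10.00% | 52.6 | 0.119 |
| 10% | 10.56% | 55.6 | 0.149 |

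The stated limit of 0.10 is passed at about 1.1%. At 2%, roughly one replaced patient in 51, it is passed slightly.

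**4. Effect on the estimate.** Suppose 8 responses in 50 evaluable patients, with 5 others replaced. Evaluable-only ORR is 8/50 = 16.0% (exact 95% CI 7.2% to 29.1%). With the 5 counted as non-responders it is 8/55 = 14.5% (6.5% to 26.7%).

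**The case against.** A reader might infer that 7.6 confines clinical progression to palliative chemotherapy or surgery, so that every early radiotherapy patient must be dropped. The text does not support that. The list in 7.6 is expressly open, the decision is the investigator's, and it also includes performance-status worsening. Nor does the plan dictate that a patient sent for surgery counts while one sent for radiotherapy to the same lesion does not; both depend on judgement. What remains is an undefined, discretionary classification.

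There are also safeguards. Section 4.3.12.1 requires a tumor assessment at the final visit, and the study calendar waives end-of-treatment imaging only if it was done in the previous 30 days. A patient leaving in week 5 will usually be scanned, and RECIST progression on that scan is a strong basis for calling the patient evaluable. Section 7.5 asks for objective progression to be documented even after treatment stops. This narrows the gap to patients with no RECIST progression on that scan who are also not called clinical progression. The symptomatic-deterioration note in 7.5 does not close it, because it names a reporting category without saying whether the patient is evaluable.

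The examples of non-evaluability in 3.6.2.1 are intolerance, unrelated illness, and unrelated trauma or death. That suggests cancer-driven rescue was not meant to be excluded, but the list is open and the general rule covers any reason other than progression.

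Section 8.4.1 is the strongest objection. A cycle is 4 weeks, so a patient who was dosed throughout and left in week 5 would be in its denominator. This stands as far as it goes. But 8.4.1 does not say that it overrides 3.6.2.1 and 4.3.12.2, those sections still decide who fills the 30 and 50 places, and patients leaving within cycle 1 are lost either way.

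Finally, no passage supports any particular frequency. The larger values of d should not be read as expected.

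**Conclusion.** The concern holds as a gap in classification. The plan makes radiotherapy or another anticancer drug a withdrawal reason distinct from progression, does not say how such a withdrawal counts for ORR, and has replacement rules that can take these patients out of the primary analysis at the discretion of an unblinded investigator. For exits before first re-staging, the effect on ORR can only be upward.

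The size is unknown. At a true ORR of 9.5%, the false-success probability is 0.100, 0.104, 0.119 and 0.149 for d of 1%, 2%, 5% and 10%, against 0.0955 with no replacement. These figures assume that every patient in d is in fact replaced, that none would have been a responder, that d is the same in both stages, and that the evaluable set is used for the decision. If 8.4.1 governed, only exits within cycle 1 would be lost and the effect would be smaller. The documents do not support reading this as forced exclusion, or as a known breach of the error rate.

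**What to change.** In 3.6.2.1, 4.3.12.2, 7.1.1 and 8.4.1, state that any treated patient withdrawn under 4.3.12 item 2 without a previously confirmed CR or PR counts as a non-responder in the primary ORR denominator and is not replaced. Report evaluable-only ORR as a sensitivity analysis.

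In the same amendment, reconcile the evaluable set of sections 3, 4 and 7 with the 8.4.1 population, including the cycle 2 versus cycle 3 window, so that one population governs the 3-of-30 and 8-of-50 rules.

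Leave the definition of clinical progression in 7.6 as it is, and note only that 7.6 and 4.3.12 item 2 must be reconciled. Making any other anticancer therapy count as progression would go too far. It could label a patient who changes drug because of toxicity as progressed, and progression also drives withdrawal, cfDNA sampling and the exemption from AE and SAE reporting in 6.3.2.

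The cost is a few sentences in four sections. ORR may come out slightly less favourable, and fewer replacement patients are needed. No treatment rule changes, and the PFS definition in 8.4.2.2, which uses RECIST progression or death, is untouched.
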